- Compound symmetry without heterogeneous variances, by visit.

The first covariance structure that converges will be used. If none of the models converge then an analysis of covariance (ANCOVA) using last observation carried forward (LOCF) imputation with similar terms as in the MMRM model (except no terms that include visit) will be used in its place. This applies to the subgroup analyses as well. This approach to analyzing continuous data will be referred to as the standard approach in the SAP.

Summary statistics will include sample size, mean, standard deviation, median, minimum, and maximum for both the actual and change from baseline measurements. Least-squares mean and standard errors derived from the MMRM model described above will also be displayed for the change from baseline measurements. Treatment comparisons will be displayed showing the

treatment difference least-squares mean and the 95% CIs for the treatment differences (dulaglutide – placebo), along with p-values for the treatment comparisons.

Unless otherwise specified, for categorical measures, summary statistics will include sample size, frequency, and percentages. Fisher's exact test will be used for treatment comparisons.

For data after Week 26 (Visit 9), the efficacy and safety data will be summarized by treatment group sequence (placebo:dulaglutide 0.75 mg, dulaglutide 0.75 mg:dulaglutide 0.75 mg, and dulaglutide 1.5 mg:dulaglutide 1.5 mg), but no inferences will be made.

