5.2. General Considerations

Statistical analysis of this study will be the responsibility of Lilly or its designee. Any change to the data analysis methods described in the protocol will require an amendment ONLY if it changes a principal feature of the protocol. Any other change to the data analysis methods described in the protocol, and the justification for making the change, will be described in the SAP or the CSR. Additional exploratory analyses of the data may be conducted as deemed appropriate.

All analyses will be conducted under the guidance and approval of Lilly statisticians.

The treatment groups mentioned in this document are dulaglutide (Dula) 1.5 mg and 0.75 mg (pooled); Dula 1.5 mg; Dula 0.75 mg; and Placebo during the double blinded period (randomization to Week 26) unless otherwise specified. Placebo becomes Placebo/Dula 0.75 mg during the open label period (Week 26 to Week 52) while the other treatment groups are unchanged.

For the purposes of tables, figures, and listings (TFLs), up to Week 26 the treatment groups will be All Dula (pooled dulaglutide doses); Dula 1.5; Dula 0.75; and Placebo. Placebo will be the reference treatment across all statistical reports whenever the treatment effect is compared between All Dula and Placebo, Dula 1.5 and Placebo, and Dula 0.75 and Placebo.

Up to Week 52 or to Week 56 (for selected safety parameters such as ADA at safety follow-up (Visit 801 [V801])), treatment will be expressed in the TFLs as All Dula, Dula 1.5, Dula 0.75, and Placebo/Dula 0.75 representing (Dula 0.75/0.75, Dula 1.5/1.5 pooled), Dula 1.5/1.5, Dula 0.75/0.75, and Placebo/Dula 0.75, respectively. No inference will be made among the treatment groups after Week 26 to Week 52 or from Week 26 to V801. Within-treatment comparisons

between different scheduled visits such as Week 26 and Week 52 for parameters such as HbA1c change (and others) from baseline may be performed.

Generally, V801 data will not be summarized unless otherwise stated, but V801 data may be listed.

Efficacy and safety data will be summarized by each treatment group at each scheduled visit unless otherwise stated.

Six patient populations are defined for the analyses in this study with detailed information listed in [Table GBGC.5.1](#).

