For continuous variables, summary statistics will include the number of patients, mean, SD, median, minimum, and maximum for both the actual and change from baseline for each treatment group at each visit. If a patient has no postbaseline data, the patient will be excluded from inferential statistical analysis. For data collected prior to first dosing, or randomization date if the first dosing date is not available, an analysis of variance (ANOVA) model with treatment (Dula 0.75, Dula 1.5, and Placebo) will be fitted. For post-first dosing longitudinal data, the aforementioned MMRM model will be fitted. For nonlongitudinal endpoint data, an ANCOVA model will be fitted by removing visit and visit-by-treatment interaction terms from its corresponding aforementioned MMRM model. Least-squares mean (LSmean) and standard errors derived from the corresponding statistical model will also be displayed for the change from baseline at each visit for each treatment group. Treatment comparisons at the same visit will be displayed showing the LSmean and the 95% CIs for the treatment differences (All Dula – Placebo; Dula 1.5 – Placebo; Dula 0.75 – Placebo) at the same visit along with the corresponding p-values up to Week 26. Appropriate estimate statements will be constructed in each aforesaid model (ANOVA, MMRM, or ANCOVA) to obtain a corresponding endpoint estimate for All Dula and the treatment comparison between All Dula and placebo at each visit of interest up to Week 26.

Unless otherwise stated, categorical variables will be summarized by sample size, frequency, and percentages for each treatment group at each visit. Fisher's exact test will be used to compare the difference among the 3 treatment groups and between All Dula and placebo.

For LOCF, the last nonmissing value will be imputed as the endpoint if the endpoint is missing. Any missing component of date and/or time may be imputed following Lilly standards.

Additional analyses may be performed even after datalock if deemed needed.

All statistical analyses will be conducted with R or SAS Version 9.4® or higher unless otherwise stated.

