Therefore, the total hypoglycemia category will have the following 2 subcategories:

1. Total Hypoglycemia (events with PG <70 mg/dL included)
2. Total Hypoglycemia (events with PG <54 mg/dL included)

The ITT population without postrescue data will be used as the population for the primary analysis for hypoglycemia.

Incidence and rates for documented symptomatic, severe, and total hypoglycemia will be summarized for a 1-year (365-day) period.

Additionally, a separate analysis will report all hypoglycemia events with PG <54 mg/dL, regardless of symptoms, and all severe hypoglycemia episodes for the ITT population, including events that occurred after patients started rescue therapy. The incidence of hypoglycemic episodes will be summarized for each treatment group for 0 to 26 weeks, 26 to 52 weeks, and 0 to 52 weeks. The summary includes the number of patients and percent of patients reporting hypoglycemic episodes for a given treatment at a certain visit interval. Fisher's exact test will be used for treatment comparison.

The rate for each category of the abovementioned hypoglycemia (PG <70 and PG <54 mg/dL if applicable) in episodes/patient/year for 0 to 26 weeks, 26 to 52 weeks, and 0 to 52 weeks will be analyzed using a negative binomial model via PROC GLIMMIX with log link function. The response is the frequency of each category of hypoglycemia of interest. The model will include stratification factors, treatment, and the interaction term of treatment by baseline insulin use as fixed effects. The logarithm of days between visits will be adjusted as an offset to account for possible unequal duration between visits and between patients. The predicted hypoglycemia rate per 1-year by treatment and visit interval will also be presented. The results will also be reported for each of the subgroups of baseline insulin use (yes, no).

The stratified Wilcoxon rank sum test will be applied for treatment comparison for all postdose intervals of interest. It will only be conducted and used as the primary analysis if the negative binomial regression analysis fails to converge.

Hypoglycemic episodes that occurred while patients are on/off insulin therapy will be summarized for the 3 categories of total hypoglycemia, documented symptomatic hypoglycemia,

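### SAP 5.15.2.1, 5.10 and 5.15.8 attach between-arm tests to data after Week 26, a period in which Protocol 12.2.1 and SAP 5.2 bar such inference and the placebo arm is on dulaglutide

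*SAP*

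**What the plan says.** **The rule.** Protocol 12.2.1 has efficacy and safety data after Week 26 summarized by treatment sequence, "but no inferences will be made". SAP 5.2 says "No inference will be made among the treatment groups after Week 26 to Week 52 or from Week 26 to V801" and allows only within-treatment comparisons between visits. Protocol 9.3 moves every placebo patient to dulaglutide 0.75 mg at Week 26, and SAP 5.2 relabels the arms accordingly for tables to Week 52: "All Dula, Dula 1.5, Dula 0.75, and Placebo/Dula 0.75 representing" the four displayed groups. The secondary safety objectives (Protocol 6.2, SAP 4.2) compare with placebo at 26 weeks and only assess the dulaglutide arms at Week 52.

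**The tests.** In SAP 5.15.2.1, hypoglycemia incidence is "summarized for each treatment group for 0 to 26 weeks, 26 to 52 weeks, and 0 to 52 weeks", and Fisher's exact test for comparing treatments follows with no limit on the window. Rates "for 0 to 26 weeks, 26 to 52 weeks, and 0 to 52 weeks will be analyzed using a negative binomial model" whose terms include treatment. The fallback reads "The stratified Wilcoxon rank sum test will be applied for treatment comparison for all postdose intervals of interest"; it runs only if the negative binomial model fails to converge. SAP 5.10 compares exposure in three windows, one of them Week 26 to Week 52, by ANOVA and promises a p-value for pooled dulaglutide against placebo. SAP 5.15.8 applies Fisher's exact test to ALT, AST and bilirubin thresholds at time points that include Week 52.

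**The general paragraph.** In SAP 5.2, model-based comparisons of continuous data are shown "at the same visit along with the corresponding p-values up to Week 26". The matching sentence for categorical data has no such words: Fisher's "exact test will be used to compare the difference among the 3 treatment groups and between All Dula and placebo".

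**The concern.** The SAP gives two instructions that cannot both be followed. A programmer working from 5.15.2.1 would produce p-values for 26 to 52 and 0 to 52 weeks; one working from 5.2 would not. Nothing in the SAP says which prevails.

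The p-values at issue also answer a different question from the safety objective. From Week 26 to Week 52 no arm is on placebo. Over 0 to 52 weeks the control arm is on placebo for half the time and on dulaglutide 0.75 mg for the other half. A test there compares randomized sequences, not dulaglutide with placebo. For an effect that persists on drug, the contrast shrinks toward the null, and a non-significant 52-week result could be misread as reassurance on hypoglycemia, which is a secondary safety objective.

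**Working it through.** The claim is about consistency of the text. The plan gives no figure for these tests and no pediatric hypoglycemia rate, so there is nothing to reproduce. The check is section against section, followed by an illustration under assumed rates.

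**1. How far the conflict reaches**

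| Place in SAP | Window and test | Status |
|---|---|---|
| 5.15.2.1 | 26 to 52 weeks: Fisher; Wilcoxon fallback; negative binomial model with treatment term | Direct conflict |
| 5.10 | Week 26 to 52: ANOVA, pooled dulaglutide v placebo p-value | Direct conflict |
| 5.15.8, liver tests | Week 52: Fisher | Direct conflict |
| 5.15.2.1 | 0 to 52 weeks: same methods | By inference from Protocol 12.2.1, because the window contains safety data from after Week 26 |
| 5.15.2.5 (allergic, hypersensitivity, injection site) | Baseline to Week 52: Fisher | By inference, as above |
| 5.15.8, calcitonin thresholds | Baseline to Week 52: Fisher | By inference, as above |
| 5.5, 5.8, 5.9, 5.15.1, 5.15.2.4, 5.15.5, 5.15.9 | Tests or p-values near Week 52 summaries, with the window or the contrast not stated | Ambiguous |

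**2. Rate ratio over 0 to 52 weeks (illustration)**

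Assume constant rates: r0 on placebo, r1 on dulaglutide (both doses alike), RR = r1/r0, and a share c of patients continuing past Week 26. The former placebo arm then has average rate (r0 + c·r1)/(1 + c), and the dulaglutide arms have r1. The observed ratio is (1 + c)·RR/(1 + c·RR).

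- c = 1: RR of 1.5, 2 and 3 become 3/2.5 = 1.20, 4/3 = 1.33 and 6/4 = 1.50. The ratio cannot exceed 2.
- c = 0.8: RR of 2 becomes 3.6/2.6 = 1.38.

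**3. Approximate power of the rate comparison**

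This is a Wald approximation at two-sided 0.05, with 50 former placebo against 100 pooled dulaglutide patients (the enrollment in SAP 5.1). It assumes a placebo rate of 1 per year, dispersion 2 and RR 2. The variance of the log ratio is (1/m0 + 2)/50 + (1/m1 + 2)/100, where m0 and m1 are expected events per patient.

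- 0 to 26 weeks: m0 = 0.5, m1 = 1.0; variance 4/50 + 3/100 = 0.110; power 55%.
- 0 to 52 weeks: m0 = 0.5 + 1.0 = 1.5, m1 = 2.0; variance 2.667/50 + 2.5/100 = 0.078; log ratio ln(1.33); power 18%.

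Over placebo rates of 0.5 to 4 per year and dispersion of 1 to 4, RR 2 gives 32% to 92% at 0 to 26 weeks and 11% to 34% at 0 to 52 weeks. The model in SAP 5.15.2.1 also has strata, a treatment-by-insulin term and censoring after rescue. These figures show dilution and do not measure that model.

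**4. Incidence by exact Fisher test, 50 v 100**

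Assume 26-week risks of 10% on placebo and 30% on dulaglutide. Over 52 weeks the former placebo arm has 1 − 0.90 × 0.70 = 37% and the dulaglutide arms 1 − 0.70 × 0.70 = 51%. The 20-point difference becomes 14 points, and power falls from 81% to 33% (40% with c = 0.8).

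**5. 26 to 52 weeks**

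Under a constant hazard the former placebo arm and the 0.75 mg arm have the same expected risk, so that contrast is about zero. Against pooled dulaglutide on the difference scale it is (r0.75 + r1.5)/2 − r0.75 = (r1.5 − r0.75)/2, a dose effect. If the doses are alike, Fisher (50 v 100, equal 26-week risks of 19% to 49%) rejects about 4% of the time, which is the size of the test.

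**The case against.** The strongest reply is that the bar in SAP 5.2 is general and already governs. This is right about scope. A reader might infer from the two sentences on continuous and categorical data that SAP 5.2 leaves Fisher tests free after Week 26. The documents do not support that: the bar is in the same section, is not restricted by type of data, and covers Fisher tests. The categorical sentence merely lacks the words that the continuous one carries. The defect is therefore a contradiction between sections, and the general rule does not remove the specific instructions in 5.15.2.1, 5.10 and 5.15.8.

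Three further points stand in part.

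- A negative binomial model with a treatment term need not yield a between-arm test; SAP 5.15.2.1 also asks for predicted rates by treatment and interval. But the fallback for that model is a rank-sum test, which gives no rates, so between-arm testing appears intended in every window. The fallback itself is conditional on non-convergence.
- SAP 5.5, 5.8 and 5.9 promise p-values against placebo, the label that SAP 5.2 uses for the double-blind period. A reader might infer a promised placebo contrast after Week 26, but the label equally supports reading those p-values as stopping at Week 26. In 5.15.9 the text does not say what the likelihood ratio p-value compares; a within-group comparison would be allowed. In 5.15.1, 5.15.2.4 and 5.15.5 the tests have no stated window. All of these need clarification and are not shown to be errors.
- A 0 to 52 week table would show the arm as the placebo/dulaglutide sequence, which lowers the risk of misreading. A sequence comparison is valid in itself; it is not a comparison with placebo.

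**Conclusion.** The conflict is real and literal in three places: hypoglycemia at 26 to 52 weeks (SAP 5.15.2.1), exposure at Week 26 to 52 (5.10) and the Week 52 liver tests (5.15.8). For the 0 to 52 week tests in 5.15.2.1, 5.15.2.5 and the calcitonin thresholds of 5.15.8 it follows by inference from Protocol 12.2.1.

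The size is illustrative, because every rate, risk and dispersion is assumed. With constant rates and everyone continuing, a rate ratio of 2 is estimated as 1.33 over 0 to 52 weeks, and the 26 to 52 week contrast with the 0.75 mg arm is about null.

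A reader might go further and infer that 52-week tests would point the wrong way, because former placebo patients start the drug at Week 26 while the others continue it. That requires events to cluster at drug start. The documents describe such a pattern for gastrointestinal symptoms (Protocol 10.4.1.2.5), but the SAP plans no 26 to 52 week test of those events, and nothing in the documents shows the pattern for hypoglycemia. Reversal is hypothetical here.

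The 0 to 26 week tests, the graphical procedure and the primary and key secondary analyses are unaffected. The plan should be corrected, but no main conclusion of the trial depends on it.

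**What to change.** Change SAP wording only:

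- In SAP 5.2, state that between-arm tests and p-values in all sections use data up to Visit 9 only, and that 26 to 52 and 0 to 52 week data are summarized by treatment sequence without between-arm p-values. The permitted within-treatment comparisons can stay.
- Add *up to Week 26* to the Fisher sentence in SAP 5.2.
- Align 5.15.2.1, 5.10, 5.15.2.5 and 5.15.8 with that rule.
- Clarify the window, or the contrast, in 5.5, 5.8, 5.9, 5.15.1, 5.15.2.4, 5.15.5 (including the Cox and log-rank analyses) and 5.15.9.

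If the sponsor wants 0 to 52 week comparisons of sequences, it should declare them as exceptions, label them as such, and reconcile them with Protocol 12.2.1 and SAP 5.2.

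The cost is that some 52-week p-values are dropped. No new data are needed.

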18. Removed hypoglycemia analyses for asymptomatic, nocturnal, and probable hypoglycemia events since they are already included in total hypoglycemia analyses, and added an additional hypoglycemia analysis, which will report all hypoglycemia events with PG <54 mg/dL, regardless of symptoms, and all severe hypoglycemia episodes for the ITT population, including events that occurred after patients started rescue therapy, since this was requested by FDA in other studies.
19. Clarified that subgroup analyses will be performed for the treatment regimen estimand only.
20. For baseline HbA1c ($\leq 8.0\%$, $>8.0\%$) subgroup analysis, added back the baseline HbA1c to the model as a covariate so that the results for actual and change from baseline are consistent, and the model terms are consistent within subgroup analyses.
21. Streamlined PRO section to reflect the latest user guide.
22. Removed the section specifying major cardiovascular events as an AE of interest since it was not included in the protocol as such, and the reporting of these events in this study population is unlikely. Any cardiovascular events that do occur should be reported as AEs and will be included in the analysis of TEAEs.
23. Updated the graphical testing scheme based on relevance of endpoints to clinicians and simulations using blinded data and published results from other trials.
24. Based on FDA feedback, the copy reference approach for multiple imputation for the primary analysis based on the treatment regimen estimand was changed to the washout method.
25. Based on FDA feedback, an interaction term of treatment by baseline insulin use was added to the negative binomial model for the analysis of hypoglycemia rates. In addition, the analyses for the incidence of hypoglycemia episodes and hypoglycemia rates will be conducted separately for the subsets of patients using insulin versus those not using insulin at baseline.

4. Study Objectives

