Unless otherwise specified, data listings will consist of all randomized patients. Both efficacy and safety analyses will be conducted using the ITT population. For safety except hypoglycemia analyses, all measurements including those made after taking rescue therapy will be included. Hypoglycemia analyses will be evaluated in the ITT population after censoring the data following administration of any rescue medication.

Unless otherwise specified, all tests of treatment effects will be conducted at a 2-sided alpha level of 0.05 and confidence intervals (CI) will be calculated at 95%, 2 sided.

For subgroup analyses, all tests of interactions between treatment and factors of interest will be conducted at a 2-sided alpha level of 0.10.

Visit 2 is the baseline visit. Baseline measurement for a corresponding parameter of interest is defined as the last nonmissing value taken prior to the first dosing of study drug. Baseline HbA1c value will be used to define HbA1c strata for analyses.

Unless otherwise specified, longitudinal continuous measures will be analyzed using MMRM with stratification factors (insulin usage [yes, no], metformin usage [yes, no], HbA1c strata [HbA1c: <8.0%, $\geq 8.0\%$]), treatment (Dula 1.5, Dula 0.75, Placebo or Placebo/Dula 0.75), visit, and treatment-by-visit as fixed effects, and corresponding baseline measurement as a covariate unless otherwise noted. The Kenward-Roger method will be used to estimate denominator degrees of freedom, and the REML approach to obtain model estimate. An unstructured covariance structure will be used to model the within-patient errors. If this model fails to converge, the following covariance structures will be tested in order:

- Toeplitz with heterogeneity
- Autoregressive with heterogeneity, by visit
- Compound symmetry with heterogeneous variances, by visit
- Toeplitz
- Autoregressive
- Compound symmetry without heterogeneous variances, by visit

The first variance-covariance structure that converges will be used.

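### The fallback for the hypoglycemia rate test is triggered only by non-convergence, which a zero-event arm-by-insulin cell normally does not cause, so the rate p-value can be meaningless without the fallback applying

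*SAP*

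**What the plan says.** SAP Section 5.15.2.1 plans summaries for several categories: "Incidence and rates for documented symptomatic, severe, and total hypoglycemia will be summarized for a 1-year (365-day) period". Those defined by plasma glucose are analyzed at both the 70 and 54 mg/dL thresholds. Rates for Weeks 0-26, 26-52 and 0-52 are "analyzed using a negative binomial model via PROC GLIMMIX with log link function". On the terms: "The model will include stratification factors, treatment, and the interaction term of treatment by baseline insulin use as fixed effects". On exposure: "The logarithm of days between visits will be adjusted as an offset". Section 5.2 lists the "stratification factors (insulin usage [yes, no], metformin usage [yes, no"] and the HbA1c stratum. With three arms, the interaction gives six arm-by-insulin cells, each with its own rate.

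The insulin subgroups are also reported: "The results will also be reported for each of the subgroups of baseline insulin use (yes, no"). The revision history (Section 3, Version 7, item 25) records that, on FDA feedback, "an interaction term of treatment by baseline insulin use was added to the negative binomial model for the analysis of hypoglycemia rates".

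Of the stratified Wilcoxon test the section says: "It will only be conducted and used as the primary analysis if the negative binomial regression analysis fails to converge". It gives no rule for a cell without events, for an extreme standard error, or for dropping the interaction, and it plans no likelihood-ratio or exact test of the rate.

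Incidence is handled separately, by Fisher's exact test (SAP 5.15.2.1; Protocol 12.2.9.2.1.1).

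**The concern.** The SAP foresees that the rate model may fail on sparse data and names a replacement, but it recognizes only one kind of failure. When a cell has no events, its maximum likelihood rate is zero and its log rate has no finite estimate. The likelihood flattens, so an optimizer normally stops and reports success. The output is then an arbitrary large number with a far larger standard error.

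The All Dula versus placebo contrast averages over insulin users and non-users, so it inherits the degenerate cell. So does the matching insulin-subgroup result. The designated rate analysis would then give p near 1 for a category in which the observed counts differ clearly. Someone would have to choose another test after unblinding, which a prespecified fallback exists to avoid.

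**Working it through.** **Inputs.** From the documents: 50 patients per arm, 1:1:1 (SAP 5.1; Protocol 9.3); the model terms, offset and trigger quoted above; two-sided alpha 0.05 (SAP 5.2). The documents give no hypoglycemia rate, insulin share, dispersion or power for this analysis, so there is no planned figure to reproduce. Assumed: 20-40% insulin users, 85% metformin users, dispersion 2, and the yearly rates in the table.

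**Why p goes to 1.** If a cell's fitted event count is m, the log rate moves with ln(m) and its standard error is about 1/sqrt(m). The Wald ratio therefore behaves like |ln m| × sqrt(m), which tends to 0 as m tends to 0. The further the optimizer runs, the closer p comes to 1.

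**Worked case 1.** 14 insulin users and 36 non-users per arm, equal follow-up. Events: placebo 0 in non-users and 5 in users; All Dula 12 and 21.
- Crude log rate ratio in users: ln[(21/28)/(5/14)] = ln 2.10 = 0.74.
- Fitted pooled contrast 11.8, SE about 18,900, convergence reported. z = 11.8/18,900 = 0.0006, p = 1.00.
- The contrast is the mean of the two log rate ratios, so the non-user value is about 2 × 11.8 − 0.74 = 22.9. That is a rate ratio of several billion, set by where the optimizer stopped.
- Without the interaction: rate ratio 3.9, p = 0.02.

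**Worked case 2.** All the SAP's terms. Placebo non-users: 0 events in 39 patients. Dulaglutide non-users: 18 events in 12 of 58 patients.
- Converged. Log rate ratio 8.69, SE 709; z = 8.69/709 = 0.012, p = 0.990.
- The empty cell has weight 1/2, so its own SE is about 1,418 and its fitted count about 1/1,418² = 5 × 10⁻⁷ events.
- At stopping tolerances 1e-6, 1e-8 and 1e-10, p = 0.915, 0.990 and 0.998.
- Same data: stratified Wilcoxon p = 0.016; likelihood-ratio p = 0.003; no-interaction model p = 0.008; Fisher p = 0.0007.
- The insulin-user contrast, which avoids the empty cell, is unaffected (p = 0.63 at every tolerance).

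**Simulation with a true increase** (250 trials per row). Rates are placebo/dulaglutide per year. The last three columns give rejection at 0.05 among trials with an empty cell.

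| Insulin users | Non-user rates | User rates | Any empty cell | Planned test | Stratified Wilcoxon | Fisher |
|---|---|---|---|---|---|---|
| 20% | 0.05/0.6 | 1.5/3 | 46% | 0% | 86% | 82% |
| 30% | 0.05/0.6 | 1.5/3 | 39% | 0% | 88% | 73% |
| 40% | 0.05/0.6 | 1.5/3 | 52% | 0% | 74% | 57% |
| 30% | 0.15/0.6 | 1/4 | 8% | 0% | 100% | 86% |
| 30% | 0.02/0.2 | 0.5/1.5 | 78% | 0% | 53% | 41% |
| 30% | 0.02/0.02 | 0.1/0.3 | 98% | 0% | 4% | 2% |

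At 0.5/1.5 in non-users and 2/5 in users, one trial in 250 had an empty cell. Every empty-cell fit reported convergence; median p ran from 0.988 to 0.999 across the rows. A separate set of refits gave 0-2% rejection for the planned test, 75-93% for Wilcoxon and 60-88% for Fisher in empty-cell trials. Further simulations put an empty cell at about 16% of trials at a placebo non-user rate of 0.1/year and at about 4% or less at 0.3/year or more.

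**The case against.** A reader might infer that a real increase in hypoglycemia would be hidden from the trial. The documents do not support that. The secondary safety objective is worded as incidence (Protocol 6.2; SAP 4.2), and Fisher's exact test has no cell to degenerate. It rejected in 41-86% of the empty-cell trials above, leaving out the near-zero row. The SAP also plans numbers and percentages of patients with episodes, a separate analysis of all events below 54 mg/dL and all severe events, events per 1000 person-years on and off insulin, and a listing of every episode. Severe events are reported as SAEs (Protocol 10.4.1.2.1). A standard error in the hundreds or thousands would be noticed. All of this stands and confines the point to the rate-model p-value.

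A reader might also infer that the loss is greatest for the rarest events. In the near-zero row the Wilcoxon test has 4% power, so almost nothing is lost there. The gap matters for categories sparse enough to empty a cell but not so sparse that no test has power.

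Three further limits stand. Hypoglycemia is outside the graphical testing scheme (SAP 5.3), and SAP 5.2 makes no between-group inference after Week 26, so Weeks 0-26 is the interval chiefly affected. PROC GLIMMIX was not run; other optimizers all reported convergence, but where GLIMMIX did not, the fallback would apply. The checks used one record per patient, whereas the offset suggests records per visit interval; a cell with no events in total has none in any interval, so the mechanism is the same.

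The remedy has also been questioned, because a Wilcoxon test on counts ignores unequal follow-up after rescue censoring. Applied to every trial with 30-40% placebo rescue at 0.3-1 event/year, its type I error was 0.07-0.11. Under the changed rule it is used only when a cell is empty, which is rare at those rates; with unequal rescue censoring that rule rejected in 3-6% of null trials overall.

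**Conclusion.** The gap is real and narrow. Non-convergence is the only trigger, a zero-event cell normally does not set it off, and the planned rate test is then uninformative for every contrast through that cell. It affects the designated rate analysis, not the incidence objective.

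How often it happens depends on rates the documents do not give. Under a true increase and the assumed placebo non-user rates, an empty cell occurred in 76-78% of trials at 0.02/year, 39-52% at 0.05, 8-16% at 0.1-0.15, and a few percent or less at 0.3 or more. It is therefore unlikely for common events such as total hypoglycemia below 70 mg/dL and more likely for events below 54 mg/dL. The mechanism itself does not rest on these assumptions; only its frequency does, together with the expectation that GLIMMIX behaves like the optimizers that were run. The change is worth making before unblinding because it is small.

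**What to change.** Extend the trigger in SAP 5.15.2.1 along these lines: *if the negative binomial model fails to converge, or if any treatment-by-baseline-insulin cell (or, in an insulin subgroup, any arm) has zero events, the stratified Wilcoxon rank sum test is the primary rate analysis for that category and interval.* State the Wilcoxon strata, which the section does not name. In those cases show event counts and crude rates by cell, and report the negative binomial model without the interaction, which keeps the exposure offset, as support. The FDA-requested interaction model stays wherever every cell has events.

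Effect of the changed trigger (400 trials per scenario, 30% insulin users; rates as placebo/dulaglutide per year):
- 0.05/0.6 in non-users, 1.5/3 in users: power 0.37 as written, 0.77 changed.
- 0.02/0.2 and 0.5/1.5: 0.04 and 0.48.
- 0.15/0.6 and 1/4: 0.75 and 0.84.
- Type I error of the changed rule in two null scenarios: 0.030 and 0.048.

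The cost is one sentence and a few lines of programming. Categories that switch lose a model-based rate ratio, which could not be interpreted there anyway, and the Wilcoxon test does not adjust for unequal follow-up after rescue censoring, hence the supporting model.
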